2.7 Biologic Rationale

Neo-adjuvant androgen ablation with radiation has demonstrated complementary response but no equivalent benefit with surgery. Several possibilities may account for these discordant observations: 1) the duration of androgen ablation in the surgical studies was insufficient, 2) the benefit reported with the combination of androgen ablation and radiation is attributed specific synergy between the modalities that do not exist with surgery and androgen ablation. Recent evidence

2015-0693 June 10, 2022 Page 12

suggests that paracrine/intracrine androgen signaling is often a driver of resistance to androgen ablation, and not inhibited by androgen ablation. Therefore the absence of specific synergies between androgen ablation and surgery as exists with radiation may account for the apparent paradox. We wish to gain evidence in support of the hypothesis that inhibition of paracrine/intracrine androgen signaling with apalutamide will improve the efficacy of surgery in some men with prostate cancer and reduce the need for postoperative radiation.

3. STUDY OBJECTIVES

3.1. Primary: To determine whether 6 months (24 weeks) of neoadjuvant apalutamide prior to prostatectomy for intermediate risk prostate cancer results in a reduction of aggregate post-operative radiotherapy risk from 35% to 15%.

3.2. Secondary:

- 3.2.1. To determine the safety and tolerability of 6 months (24 weeks) neoadjuvant apalutamide followed by radical prostatectomy for intermediate risk prostate cancer
- 3.2.2. To estimate the frequency of clinical complete responses and "near" complete responses (currently defined as <6mm total tumor volume)
- 3.2.3. To characterize the molecular features of the treated prostate cancers and link them to morphologic characterization
- 3.2.4. To measure the 3-5 year biochemical recurrence rate and quality of life of treated patients as a baseline to inform a larger phase III trial.

4. INVESTIGATIONAL PLAN

This is a single center, phase II, open label, pre-operative study of apalutamide in patients with intermediate risk prostate cancer. The study period will consist of screening, treatment, and follow-up visits to 12 months post-operative. Additional follow-up onsite or via remote contact will determine disease-free and treatment-free status at yearly intervals 2-5. Surgery will occur within 2 weeks of completing 24 weeks of apalutamide. At the mid-way evaluations (weeks 9 or 12), patients who fail to reach a ≥50% decrease in PSA, or demonstrate suspicious changes in DRE will be considered non-responders and recommended for early surgery. For responders, the plan calls for 5 pre-operative PSA measurements that will be analyzed for rate of decline and nadir. In the post-treatment evaluation, patients will be off formal protocol at 12 months, however the investigating team will track PSA measurements for biochemical failure rates at 2, 3, 4 and 5 years (outside or inside measurements) using >0.2 ng/mL as the failure definition.

5. PATIENT POPULATION

5.1. Inclusion Criteria

- Willing and able to provide written informed consent
- Male, age > 18 years
- Histologically confirmed adenocarcinoma of the prostate
- A minimum of 10 core biopsies have been performed at baseline and available. A prostate biopsy within 6 months from screening is allowed for entry requirements. Biopsies performed within 6-12 months from screening are acceptable if the treating physician would allow treatment without further biopsy. Patients must meet intermediate risk criteria from Gleason score, T stage, and PSA value by NCCN criteria: cT2b-T2c or Gleason 7 (3+4 or 4+3) or PSA 10-20 ng/mL. In addition, the Gleason 3+4 or 4+3 must be present.
- Pathology review at MD Anderson Cancer Center. The volume of disease must be high enough for the surgeon to agree to include an extended template pelvic lymph node dissection.
- Serum testosterone > 200 ng/mL
- Patient and urologist must agree that patient is suitable for prostatectomy
- No evidence of metastases on imaging. This risk group does not require metastatic studies, but if performed they must be negative (as determined by urologist or radiologist). Suspicious lymph nodes permissible if < 10 mm.
- Eastern Cooperative Oncology Group (ECOG) Performance Status 0 or 1.
- Hemoglobin ≥ 10.0 g/dL
- Platelet count ≥ 100,000 x 10⁹/microliter,
- GFR >45 mL/min
- Serum potassium ≥ 3.5 mmol/L
- Serum albumin ≥ 3.0 g/dL
- Able to swallow the study drug whole as a tablet
- Liver function test with serum bilirubin < 1.5x ULN and ALT and AST < 2.5 x ULN Note: In subjects with Gilbert's syndrome, if total bilirubin is >1.5 × ULN, measure direct and indirect bilirubin and if direct bilirubin is ≤1.5 × ULN, subject may be eligible
- Normal coagulation profile and no history of substantial non-iatrogenic bleeding diathesis
- Agrees to use a condom (even men with vasectomies) and another effective method of birth control if he is having sex with a woman of childbearing potential or agrees to use a condom if he is having sex with a woman who is pregnant while on study drug and for 3 months following the last dose of study drug. Must also agree not to donate sperm during the study and for 3 months after receiving the last dose of study drug.

5.2. Exclusion Criteria

- Histological variants in the primary tumor, other than adenocarcinoma; for example: neuroendocrine tumor, small cell or sarcomatoid
- Serious or uncontrolled co-existent non-malignant disease, including active and uncontrolled infection

- PSA is > than 20 ng/mL (NOTE: unless other valid PSAs were ≤ 20 and the treating physician considers a value > 20 related to the biopsy or other nonmalignant cause. The treating physician must consider the patient intermediate risk in aggregate.)
- Uncontrolled hypertension. Patients with a history of hypertension are allowed provided blood pressure is controlled by anti-hypertensive therapy. Note that this is NOT a criterion related to particular BP results at the time of assessment for eligibility, nor does it apply to acute BP excursions that are related to iatrogenic causes, acute pain or other transient, reversible causes.
- Active or symptomatic viral hepatitis or chronic liver disease.
- Clinically significant heart disease as evidenced by myocardial infarction, arterial thrombotic events in the past 6 months, severe or unstable angina, or Class III-IV New York Heart Association heart failure.
- Other malignancy, except non-melanoma skin cancer, that is active or has a
 ≥ 30% probability of recurrence within 12 months
- History of gastrointestinal disorders (medical disorders or extensive surgery)
 which may interfere with the absorption of the study drug
- Known history of pituitary and/or adrenal disease (or dysfunction)
- Prior hormone therapy for prostate cancer including orchiectomy, antiandrogens, ketoconazole, or estrogens (5-α reductase inhibitors allowed), or LHRH agonists/antagonists
- Severely compromised immunological state, including being positive for the human immunodeficiency virus (HIV)
- Patients who are not appropriate surgical candidates for radical prostatectomy based on the evaluation of co-existent medical diseases and competing potential causes of death (such as but not limited to, unstable angina, myocardial infarction within the previous 6 months, or use of ongoing maintenance therapy for life-threatening ventricular arrhythmia, uncontrolled hypertension)
- History of seizure, seizure disorder, or any condition that may predispose to seizure including, but not limited to underlying brain injury, stroke, primary brain tumors, or brain metastases. Also, history of loss of consciousness or transient ischemic attack within 12 months of enrollment (Day 1 visit). Drugs may not be used which are known to decrease the seizure threshold.

6. STATISTICAL METHODS

The primary objective of the study is to determine whether 6 months of neoadjuvant apalutamide prior to prostatectomy for intermediate risk prostate cancer can result in a reduction of "aggregate pathologic risk features" (APRF) that drive post-operative radiotherapy recommendations. We hypothesize a reduction of 20% (i.e., from 35% to 15%) in terms of the rate of APRF among intermediate risk patients. Using a one-sample exact binomial test and with a two-sided type I error of 0.05, a sample size of 41 patients would provide 84% power to detect this change. We would factor up to

10% additional enrollment for compliance issues, thus the total enrollment from MDACC will be up to 45 patients.

6.1. Endpoints of Study

6.1.1. **Primary Endpoint**

The primary endpoint, aggregate pathologic risk features, is defined as any of the 3 pathologic staging features on a radical prostatectomy specimen that indicate elevated future risk of a patient needing pelvic radiation therapy. It can be any single or combination of the three. The three drivers per AUA/ASTRO guidelines are positive surgical margins, extraprostatic extension, and/or seminal vesicle invasion. These will be determined by a single expert genitourinary pathologist. The primary objective is to show a 20% decrease in these aggregate pathologic features.

6.1.2. **Secondary Endpoints**

- To determine safety and tolerability of 6 months neoadjuvant apalutamide followed by radical prostatectomy for intermediate risk prostate cancer
- To estimate the frequency of clinical complete responses (pT0) and "near" complete responses (<6mm total tumor volume)
- To characterize molecular features of treated prostate cancer and link them to morphologic characterization
- To measure 3-5 year biochemical recurrence rate and quality of life of treated patients as a baseline to inform a larger phase III trial.

6.2 Analysis Plan

All patients who receive at least 9 weeks of neoadjuvant therapy of apalutamide and undergo radical prostatectomy will be evaluable for the primary endpoint of APRF. The proportion of patients with APRF will be estimated by the number of patients with APRF divided by the total number of evaluable patients. As a primary analysis, we will estimate this proportion along with the exact 95% confidence interval. All patients who receive any dose of apalutamide will be evaluable for safety. Toxicity data will be summarized by category, grade and attribution. Frequency distributions, graphical techniques and other descriptive measures will form the basis of the analysis of safety data.

The proportion of patients having clinical complete responses and "near" complete responses will be estimated, along with the exact 95% confidence interval. The molecular features of the treated patients will be characterized using descriptive statistics and their association with the primary endpoint, APRR, or

clinical response will be assessed through logistic regression analyses. The Kaplan-Meier method will be used to assess time to biochemical recurrence and to estimate the rate of biochemical recurrence at various time points. The EPIC quality of life data will be summarized by domains and will be compared pre- and post-treatment using paired t-test or Wilcoxon signed rank test as appropriate.

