- Concomitant Medications Review
- Adverse Events

Note: At the mid-way evaluation (week 9), patients who fail to reach a 50% decrease in PSA, or demonstrate suspicious changes in DRE will be considered non-responders and recommended for early surgery.

4) Week 12 Procedures (± 3 days):

Optional: Repeat prostate biopsy per urologist's discretion. Acceptable to perform at the week 9 or week 17 visit if requested for patient travel needs.

5) Week 17 Procedures (± 3 days):

- Medication dispensing (neoadjuvant apalutamide)
- Dosing compliance
- Physical exam with DRE if indicated by treating physician
- Vital signs
- ECOG Performance Status
- Laboratories (Serum chemistry and hematology)
- Thyroid Stimulating Hormone (TSH) (T3 and T4 only to be done if TSH is abnormal)
- Prostate-Specific Antigen (PSA) Test and Testosterone
- Concomitant Medications Review
- Adverse Events
- EPIC Quality of Life (QOL) Questionnaire
- Blood collection for Correlative Studies

6) Week 24/ Pre-op/ End of Treatment Visit Procedures (± 3 days):

- Dosing compliance
- Physical exam with DRE
- Vital signs
- ECOG Performance Status
- Laboratories (Serum chemistry and hematology)
- Thyroid Stimulating Hormone (TSH) (T3 and T4 only to be done if TSH is abnormal)
- Prostate-Specific Antigen (PSA) Test and Testosterone
- Concomitant Medications Review
- Adverse Events
- EPIC Quality of Life (QOL) Questionnaire

- Blood collection for Correlative Studies
- 7) Radical Prostatectomy (2 weeks (+/-7 days) after last dose of study drug):
 - Perioperative data collection
 - Pathology Tissue Collection

C. Follow-up Phase:

- 1) Post Radical Prostatectomy: (within 30 days post-op +/- 3 days)
 - Physical exam and DRE if indicated by treating physician
 - Assess complications from surgery at 30 days using Clavien methodology (Table 5).
 - Adverse Events
 - Epic Quality of Life (QOL) Questionnaire
 - PSA, testosterone
- 2) Six Months Post-Radical Prostatectomy: (+/- 4 weeks)
 - a. Update complications to 90 day window
 - b. Use of adjuvant/salvage therapies
 - c. EPIC Quality Of Life (QOL) Questionnaire
 - d. PSA, testosterone
- 3) Twelve Months Post Radical Prostatectomy—Last on-site Study Visit: (+/- 4 weeks)
 - a. EPIC Quality Of Life Questionnaire
 - **b.** PSA, testosterone
 - c. Use of adjuvant/salvage therapies
 - d. Update complications
- 4) Post Study Follow-up Data Collection (on-site or remote): (+/- 4 weeks)
 - **a.** Intervals 24, 36, 48, 60 months

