ECOG PS	Х	Χ	Χ	Χ		Χ	Х								
EKG	Х														
MRI Pelvis	Χi														
Concomitant Medication	Х	Х	Х	Х		Х	Х			Xc	Xc	Xc	Χc	Xc	Xc
AE	Х	Х	Х	Χ		Х	Х		Х						
Dosing compliance			Х	Х		Х	Х								
Serum chemistry/ hematology ^d	Х	Х	Х	Х		Х	Х								
PT/PTT	Х														
TSH ^e	Х	Х	Х	Χ		Х	Х								
PSA	Х	Х	Х	Х		Х	Х		Х	Х	Х	Х	Х	Χ	Χ
Testosterone	Х	Х	Х	Х		Х	Х		Х	Х	Х				
EPIC QOL	Х					Х	Х		Х	Х	Х	Х	Х	Χ	Χ
Blood Correlative Studies ⁱ	Х					Х	Х								
Tissue procurement	Χ ^f				Xf			Х							
Complications, post op therapy ⁹									Х	Х	Х	Х	Х	Х	Х

- a: Within 30 days prior to initiation of study treatment
- b: Physical exam and DRE if indicated by treating physician
- c: Use of adjuvant/salvage therapies only, such as hormones or radiation
- d: albumin, calcium, lactate dehydrogenase (LDH), sodium, potassium, chloride, magnesium, carbon dioxide, creatinine, BUN, AST, ALT, alkaline phosphatase, total bilirubin, total protein, glucose, complete blood count with differential
- e: T3/T4 testing to be done if abnormal TSH or clinically indicated
- f: Optional collection of tissue for research purposes at time of prostate biopsy at baseline and week 12, if indicated by treating physician. If patient is not available to return to clinic on week 12 for repeat biopsy, this could be done either during week 9 or week 17 visits. Please note that tissue collection at time of radical prostatectomy is mandatory
- g: Record post-operative complications using Clavien method within 30 days and 90 days, and any long-term complications related to surgery.

- h: Early treatment discontinuation patients will complete all the pre-op assessments within 30 days post treatment discontinuation as their last study visit
- i: Including plasma, whole blood and serum samples as indicated in section 9.1
- j. As per physician discretion

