To discontinue Study Treatment, either of the criteria below must be met:

- The patient completed 24 weeks of study treatment;
- Patients who fail to reach a 50% decrease in PSA or demonstrate suspicious changes in DRE at mid-way evaluation (week 9);
- Sustained side effects: patients who have sustained toxicities, such as
 hyperglycemia or hypertension that do not return to NCI CTCAE (version 4.0)
 grade 1 or less within 30 days despite appropriate medical management,
 should be discontinued from the study treatment phase. All end-of-study
 treatment procedures should be conducted. The patient will be followed to the
 pre-op visit;
- Dosing noncompliance: study treatment administration and dosing compliance will be assessed on Day 1 of all cycles, and at Pre-surgery/End of Treatment Visit. A count of study treatment will be conducted during this visit and patient dosing compliance will be assessed. If dosing compliance is not >75% in the absence of toxicity, patient should be re-instructed regarding proper dosing procedures and continue in the protocol. Subsequent dosing compliance procedure will be conducted at each study visit. If a patient misses 14 or more doses within 4 weeks, the patient should be discontinued from the study treatment phase. All end-of-study treatment procedures should be followed. The patient will be followed to the pre-op visit
- Initiation of new anticancer treatment: patients will be discontinued from the study treatment when investigator, in his or her judgment, determines new treatment for prostate cancer is warranted. All end-of-study treatment procedures should be conducted and the patient will be followed to the preoop visit
- Administration of prohibited medications: the patient will be discontinued from the protocol treatment when prohibited drug is administered (Section 8.1.4.3).
 All end-of-study treatment procedures should be conducted and the patient

2015-0693 June 10, 2022 Page 39

will be followed to the pre-op visit. Supportive care medications are permitted with their use following institutional guidelines. The concurrent administration of other anticancer therapy, including cytotoxic, hormonal (except LHRHa), or immunotherapy is prohibited during study treatment phase. Use of other investigational drug therapy for any reason is prohibited

- Patient met Grade 4 criteria for elevated Liver Function Tests or the criteria for dose discontinuation of non-mineralocorticoid based side effects.

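### Men stopped for poor PSA or DRE response at week 9 can fall short of the 9 weeks of drug that section 6.2 requires, and so drop out of the primary denominator

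*Combined protocol and SAP*

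**What the plan says.** **Who counts.** Section 6.2: "All patients who receive at least 9 weeks of neoadjuvant therapy of apalutamide and undergo radical prostatectomy will be evaluable for the primary endpoint". The APRF proportion is events over evaluable men, reported with an exact 95% interval. Section 6.2 plans no APRF analysis of all operated men.

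**Who stops at week 9.** The discontinuation criteria in section 8.2.4 include "Patients who fail to reach a 50% decrease in PSA or demonstrate suspicious changes in DRE at mid-way evaluation (week 9". The week 9 note in section 7.1 says that "patients who fail to reach a 50% decrease in PSA, or demonstrate suspicious changes in DRE will be considered non-responders", and recommends early surgery for them. Section 4 is looser on timing: "At the mid-way evaluations (weeks 9 or 12), patients who fail to reach a ≥50% decrease in PSA". The calendar (Table 6) schedules no PSA at week 12.

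**Timing.** Drug is first dispensed at Week 1, with later dispensing visits at Weeks 5, 9 and 17. The Week 9 visit has a ± 3 day window. No section gives it a day number. The Radical Prostatectomy part of 8.2.4 places surgery within 2 weeks of stopping drug, so a man stopped at week 9 is still expected to yield a specimen.

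**Design.** Section 6 tests APRF of 35% against 15% with an exact binomial test at two-sided 0.05, and gives 84% power with 41 men. Enrolment allows for "10% additional enrollment for compliance issues, thus the total enrollment from MDACC will be up to 45 patients".

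**The concern.** The stopping point for poor responders sits almost on the evaluability cut-off, so a few days of scheduling can decide whether such a man counts. Whether he reaches that point depends on his response to treatment, measured after treatment began. The 35% comparator in section 2.1 comes from surgical series in which nobody was removed for drug response. If poor responders have more APRF than responders, leaving them out lowers the estimate for a reason other than drug effect, and a single-arm trial has no control group to reveal it. If their APRF is the same, there is no bias. Because 45 may be enrolled for a target of 41, up to 4 men could be lost this way with the target still met.

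**Working it through.** **1. The plan's own figure.** With n = 41 and 0.025 in the lower tail, the test rejects 35% at 8 or fewer events: P(X ≤ 8 | 41, 0.35) = 0.0240. Power is P(X ≤ 8 | 41, 0.15) = 0.848, in line with the stated 84%.

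**2. Days of drug before the visit.** Required: 9 × 7 = 63. Days of drug = visit day − 1.

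- Week 1 = Day 1: Week 9 starts on Day 57, and the window is Days 54-60. Exposure is 53-59 days, short by 4-10 days on every day of the window. The reference in 8.2.4 to compliance checks on the first day of each cycle fits this numbering.
- Completed weeks: Week 9 is Day 64, and the window is Days 61-67. Exposure is 60-66 days. Days 61, 62 and 63 give 60, 61 and 62 days, so 3 of the 7 days fall short. The visit titled "Week 24/ Pre-op/ End of Treatment Visit Procedures", which closes 24 weeks of drug, fits this numbering.

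A man stopped at the visit can therefore fall short under either reading.

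**3. Effect on the chance of a false success.** Assumptions, none given in the documents: 45 men operated on; overall APRF 35% (no drug effect); k stopped men left out; APRF among them q = 50-80%.

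- Expected events overall: 45 × 0.35 = 15.75.
- APRF in the remaining men: r = (15.75 − kq)/(45 − k). Example, k = 4 and q = 0.8: (15.75 − 3.2)/41 = 30.6%.
- Critical count c (largest with lower tail ≤ 0.025 at 35%): 8 for n = 41 to 44, and 9 for n = 45.
- Left out: error = P(X ≤ c | 45 − k, r).
- All counted: error = Σ over j of P(j events among k at rate q) × P(X ≤ 9 − j | 45 − k, r).

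| Left out (k) | r at q = 50% / 80% | Error, left out, q = 50% / 80% | Error if q = 35% (no bias) |
|---|---|---|---|
| 1 | 34.7% / 34.0% | 0.0131 / 0.0166 | 0.0117 |
| 2 | 34.3% / 32.9% | 0.0188 / 0.0291 | 0.0149 |
| 3 | 33.9% / 31.8% | 0.0265 / 0.0495 | 0.0190 |
| 4 | 33.5% / 30.6% | 0.0370 / 0.0812 | 0.0240 |

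Counting all 45 gives 0.017-0.022 over the same range. The expected estimate, 35% − r, falls by 0.3-1.0 points with 1 man left out and by 1.5-4.4 points with 4.

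**4. Effect on power.** Assume responders have 15% APRF and stopped men 35%.

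| Stopped men | All 45 counted | Stopped men left out |
|---|---|---|
| 1 | 85.4% | 79.4% |
| 2 | 83.4% | 81.3% |
| 4 | 78.9% | 84.8% |

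**The case against.** **The cut-off may have been meant to keep these men in.** Sections 6.2, 7.1 and 8.2.4 all use the number 9, and the natural purpose is to make the week 9 evaluation the minimum for evaluability. This is plausible, but the text does not say it. On the Day 57 numbering the rule does the opposite, and on the completed-weeks numbering it does so for part of the window. If this was the intent, the fix simply states it.

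**Drug need not stop on the visit day.** The PSA is drawn at week 9, drug is dispensed at the same visit, early surgery is only recommended, and section 4 mentions week 12. This stands: some men would pass 63 days, and a reader should not infer that every week 9 non-responder is excluded. Scheduling would still decide who counts.

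**Few men will fail the check.** This also stands. In the enzalutamide monotherapy study described in section 2.5, the median maximum PSA decline was 100%, mostly within 5 weeks. The documents give neither the share of poor responders nor their APRF.

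**Two stronger readings are not supported.** A reader might infer that leaving out a single man could manufacture a success. With 45 operated, it cannot. The limit is 8 of 44 without him (tail 0.0117) and 9 of 45 with him (0.0220). If the other 44 have 8 events and he adds one, 9 of 45 still succeeds. A reader might also infer from calendar footnote h ("Early treatment discontinuation patients will complete all the pre-op assessments within 30 days post treatment discontinuation as their last study visit") that these men's specimens go unread. The footnote concerns clinic assessments, and footnote f says: "Please note that tissue collection at time of radical prostatectomy is mandatory". Nothing stops the pathology being read for APRF.

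**Conclusion.** The gap is real. Applied literally, section 6.2 can drop operated poor responders from the primary denominator under either reading of week 9, unless they keep taking drug to day 63 or are evaluated at week 12.

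The likely effect is small. Leaving out one man gives a lower error (0.013-0.017) than counting him (about 0.021). Two men pass 0.025 only towards the top of the assumed APRF range. A material excess needs 3-4 such men, 7-9% of 45, all with high APRF. These sizes rest on the assumed counts and rates in the working, and the bias disappears if stopped men have the same APRF as the rest.

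A reader might conclude that the primary test is invalid or the sample size wrong. The documents support neither: the stated power reproduces. The change is worth making because a stated rule can exclude men on a post-treatment response marker, and the remedy uses data already collected.

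**What to change.** Add to section 6.2: *A man whose apalutamide is stopped under the week 9 PSA/DRE rule and who undergoes radical prostatectomy is evaluable for APRF, whatever his number of days on drug.* Report the number of such men and their APRF separately. The week 9 rule stays as it is, as does the 9-week requirement for men who stop for other reasons.

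The cost is one sentence and one reported line, with no extra visit or test. The downside is that a few men with shorter exposure are counted, and the estimate may be slightly less favourable. If responders have 15% APRF and stopped men 35%, power is 79% rather than 85% with 4 such men, but 85% rather than 79% with 1.

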6.3 Interim Analysis

The standard therapy for intermediate risk prostate cancer patients is radical prostatectomy. In the current trial, we are treating patients with apalutamide for 6 months in the neoadjuvant setting followed by the standard radical prostatectomy, thus we do not anticipate the rate of APRF(aggregate pathologic risk features) to be higher than the 35% rate with radical prostatectomy alone. Therefore, no interim analysis for futility is planned.

Monitoring for safety will be implemented in this single arm trial with the benchmark of avoiding extreme toxicities (TOX), defined as any adverse event preventing surgery or treatment-related death before surgery. Patients who voluntarily leave the trial for any reasons, or are successfully treated with dose reductions and proceed with surgery will not be counted as having a TOX. Denote the probability of TOX by θ_T and a beta(0.6, 1.4) distribution was assumed for the prior. Our stopping rule is given by the following probability statement: Pr ($\theta_T > 0.30$ | data) >0.90. That is, we will stop the trial if, at any time during the study, we determine that there is more than a 90% chance that the TOX rate is more than 30%. The corresponding stopping boundaries are shown in Table 1 below and the operating characteristics of the toxicity monitoring are illustrated in Table 2. Multc Lean Desktop (v2.1.0) was used for generating the stopping boundaries and the OC table.

Table 1. Interim toxicity stopping boundaries in cohort size of 5.

Among These Number of	Stop the trial if these many
Patients	patients with toxicities
5	4-5
10	6-10
15	8-15
20	9-20
25	11-25
30	13-30
35	15-35
40	16-40
45	18-45

Table 2. The operating characteristics of toxicity monitoring.

True Toxicity Rate	Prob (stop early)	Average number of patients
0.1	0.0006	44.98
0.2	0.02	44.32
0.3	0.21	39.70
0.4	0.66	28.55
0.5	0.95	17.57

An Efficacy/Toxicity Summary will be submitted after the first five evaluable patients complete 24 weeks of study treatment, and every five patients thereafter. The Investigator is responsible for completing the summary report and submitting it to the IND Office Medical Monitor for review.

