- Important medical events that may not result in death, be life-threatening, or require hospitalization may be considered a serious adverse drug experience when, based upon appropriate medical judgment, they may jeopardize the patient or subject and may require medical or surgical intervention to prevent one of the outcomes listed in this definition. Examples of such medical events include allergic bronchospasm requiring intensive treatment in an emergency room or at home, blood dyscrasias or convulsions that do not result in inpatient hospitalization, or the development of drug dependency or drug abuse (21 CFR 312.32).
- Important medical events as defined above may also be considered serious adverse events. Any important medical event can and should be reported as an SAE if deemed appropriate by the Principal Investigator or the IND Sponsor, the IND Office.

NOTE: DEATH FOR ANY REASON SHOULD BE REPORTED AS A SERIOUS ADVERSE EVENT.

Hospitalization

For reports of hospitalization, it is the sign, symptom or diagnosis which led to the hospitalization that is the serious event for which details must be provided.

Any event requiring hospitalization or prolongation of hospitalization that occurs during the study must be reported as a serious adverse event, except hospitalizations for the following:

- Hospitalizations not intended to treat an acute illness or adverse event (e.g., social reasons such as pending placement in long-term care facility)
- Surgery or procedure planned before entry into the study. [Note:
 Hospitalizations that were planned before the start of data collection and
 where the underlying condition for which the hospitalization was planned has
 not worsened will not be considered serious adverse events. Any adverse
 event that results in a prolongation of the originally planned hospitalization is
 to be reported as a new serious adverse event.]

Life-Threatening Conditions

Disease progression should not be recorded as an adverse event or serious adverse event term; instead, signs and symptoms of clinical sequelae resulting from disease progression/lack of efficacy will be reported if they fulfill the serious adverse event definition.

Unexpected (Unanticipated) AE - Any AE, with specificity or severity that is not consistent with the current IB, or the applicable product reference safety information, or not consistent with the risk information described in the informed consent document or general investigational plan.

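### The primary APRF rate counts only men who undergo prostatectomy, and no analysis accounts for treated men who are never operated

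*Combined protocol and SAP*

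**What the plan says.** Section 6.1.1 defines APRF on the prostatectomy specimen. Section 6.2 says that men with at least 9 weeks of apalutamide "and undergo radical prostatectomy will be evaluable for the primary endpoint of APRF", and divides the number with APRF by the number evaluable. Safety, by contrast, covers every man who takes any dose.

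Section 6 sets the target: "We hypothesize a reduction of 20% (i.e., from 35% to 15%) in terms of the rate of APRF among intermediate risk patients". The test is described as "Using a one-sample exact binomial test and with a two-sided type I error of 0.05", and "a sample size of 41 patients would provide 84% power to detect this change". Enrolment rises to 45 through "10% additional enrollment for compliance issues".

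Several provisions bear on men who stop early:
- Sections 4 and 7.1: men without the required PSA fall, or with suspicious DRE changes, are recommended for early surgery.
- Section 8.1.3: men off drug for more than 30 days because of toxicity are scheduled for surgery.
- Section 8.2.4, Criteria for Discontinuation of Study Treatment: "patients will be discontinued from the study treatment when investigator, in his or her judgment, determines new treatment for prostate cancer is warranted". These men, and those stopped for sustained side effects or noncompliance, are followed to the pre-op visit.
- Section 8.2.4, Withdrawal from Study: men may withdraw, the reason is documented, and replacement is possible if completers fall short of the required number.
- Section 6.3: TOX is "defined as any adverse event preventing surgery or treatment-related death before surgery", and men who leave voluntarily are not counted.
- Section 8.2.1: "Disease progression should not be recorded as an adverse event or serious adverse event term", although clinical sequelae of progression are reported if they meet the SAE definition.

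**The concern.** The 35% benchmark comes from surgical pathology series (Section 2.1), in which every man was operated. In this trial surgery follows 24 weeks of drug and up to about two further weeks. Men can leave in that interval, and the protocol foresees that some will. A man who is never operated has no APRF result and drops out of both numerator and denominator.

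If such men have worse disease than those who stay, the operated group is a favourable selection and its APRF rate falls without any drug effect. Replacement does not repair this, because it refills the denominator with operated men. The 10% allowance covers numbers, not selection. Section 6.2 contains no all-treated analysis, failure rule or sensitivity analysis that would show the reader how much this matters.

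**Working it through.** **Inputs.** From Section 6: null rate 0.35, target 0.15, n = 41, two-sided 0.05 (0.025 in the lower tail), enrolment up to 45. The documents give no no-surgery rate. I assume d = 1 to 4 of 45, where 4 = 45 − 41.

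**The plan's own figure.** With X ~ Bin(41, p), the largest c with P(X ≤ c | 0.35) ≤ 0.025 is c = 8.
- P(X ≤ 8 | 0.35) = 0.0240
- P(X ≤ 8 | 0.15) = 0.848

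This reproduces the stated 84%.

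**False-positive rate with no drug effect.** Let 35% of all 45 treated men be adverse (0.35 × 45 = 15.75). Let d men never reach surgery, a fraction q of them adverse. The rate among operated men is then p = (15.75 − q·d)/(45 − d), and the trial succeeds with probability P(X ≤ 8 | 45 − d, p).

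Four men lost (41 operated):

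| q | p among operated | P(success) |
|---|---|---|
| 35% | 35.0% | 2.4% |
| 50% | 13.75/41 = 33.5% | 3.7% |
| 60% | 13.35/41 = 32.6% | 4.9% |
| 80% | 12.55/41 = 30.6% | 8.1% |
| 100% | 11.75/41 = 28.7% | 12.9% |

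Fewer men lost, all adverse (rule ≤ 8 among those operated). The last column is the same rule at p = 0.35, that is, with uninformative loss:

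| d | p among operated | P(success) | At p = 0.35 |
|---|---|---|---|
| 1 | 14.75/44 = 33.5% | 1.9% | 1.2% |
| 2 | 13.75/43 = 32.0% | 3.9% | 1.5% |
| 3 | 12.75/42 = 30.4% | 7.3% | 1.9% |

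**Tipping point with 41 operated and 4 not.** Among all 45, the upper exact 95% limit stays below 35% up to 9 adverse men: 9/45 = 20.0% has an upper limit of 34.6%, and 10/45 = 22.2% has the interval 11.2% to 37.1%. An operated-only result of k/41 therefore tips when k plus the lost men counted as adverse reaches 10.

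| Operated only | Exact 95% CI | Lost men needed to tip |
|---|---|---|
| 8/41 = 19.5% | 8.8–34.9% | 2 |
| 7/41 = 17.1% | 7.2–32.1% | 3 |
| 6/41 = 14.6% | 5.6–29.2% | 4 |
| 5/41 or fewer | | none of 0 to 4 |

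If all four count, 8/41 becomes 12/45 = 26.7% (14.6–41.9%).

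**Price of the worst-case count.** If 4 men are lost and the true rate among operated men is 15%, the all-treated interval excludes 35% only when at most 9 − 4 = 5 of 41 have APRF: P(X ≤ 5 | 41, 0.15) = 0.41. The expected all-treated rate is (0.15 × 41 + 4)/45 = 22.6%.

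**The case against.** The strongest reply is that the evaluable set matches both the endpoint and the benchmark. APRF needs a specimen, and the 35% comes from specimens. Counting a man without surgery as APRF compares a composite (pathology or no surgery) with a pathology-only figure, which is biased against the drug. A man who leaves for personal reasons has no margin, extraprostatic or seminal vesicle finding. This stands, and it is why the evaluable-patient analysis should remain primary.

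A reader might infer that the worst outcomes cannot count against the drug at all. The documents do not support that. PSA/DRE non-responders and men off drug for prolonged toxicity are directed to surgery, noncompliant men are followed to the pre-op visit, and all of them enter the APRF rate if operated after at least 9 weeks of drug. Starting a new anticancer treatment stops study drug, but the text does not say that surgery is cancelled.

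A reader might also infer from "Disease progression should not be recorded as an adverse event or serious adverse event term" that a man whose surgery is abandoned for progression is invisible to both efficacy and safety. That is too broad. Serious clinical sequelae of progression are reportable, and one that prevents surgery can reach the TOX rule. Only voluntary departures and progression without such sequelae reach neither.

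Finally, 4 lost men is a pessimistic assumption: Section 6 labels the allowance as compliance, and noncompliant men are still followed to the pre-op visit. The full range above therefore matters more than its upper end.

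**Conclusion.** The gap is real and limited. It concerns treated men who are never operated, and the plan has no efficacy analysis that includes them. Adverse events that prevent surgery can trigger the safety rule but cannot affect the efficacy result.

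The direction of bias is downward only if loss is related to poor outcome. If it is unrelated, the false-positive rate stays at 2.4%. With 4 lost it reaches 12.9% if all are adverse; with one or two lost it stays at or below 3.9%. These figures assume 45 treated, no drug effect, and a loss count and adverse fraction that the documents do not supply. Results at or near the rejection boundary are fragile (2 men at 8/41), whereas 5/41 or fewer is secure against all four. Because so few men can decide the matter in an open-label single-arm trial, the handling should be fixed before results are known.

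**What to change.** Keep the evaluable-patient analysis as primary and add to Section 6.2:

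> A supportive analysis will include every patient who received apalutamide, counting patients without prostatectomy as having APRF (worst case), with the exact 95% CI. The number of non-operated patients who would have to be counted as APRF to change the conclusion, and the number and reasons for no surgery, will be reported.

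Do not make this a second success criterion. As a hurdle it would be passed with probability only 0.41 at the 15% target if 4 men are lost, against 0.85 for the primary rule.

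The cost is two sentences and one table. No new patients are needed, and withdrawal reasons are already to be documented. The downside is that the supportive estimate is conservative and less favourable than the primary one, and it should be labelled as a worst case.
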